The risk of serious side effects of respiratory depression with concomitant use with opioids is acknowledged (BC Children's Hospital Integrated Pain Service Gabapentin Information http://www.bcchildrens.ca/Pain-Services-Site/Docu-Sheet. Accessed at: ments/BCCH1455Gabapentin.pdf. Retrieved on October 4, 2020). A minority of patients might be on opioids. Dose adjustments will be added when gabapentin is used with a concomitant opioid or other CNS depressant medication: the family will be advised to return to the previous stable, safe dose in the protocol, and the subject will remain at that dose with no further escalation for the duration of the trial arm. This schedule will be duplicated on the parallel arm (active drug or placebo) to maintain masking. The participants are highly monitored, often with continuous oxygen saturation monitoring and/or "baby-cam" devices observing them during sleep. During the daytime they are with family, or professional caregivers (aides, nurses, etc.). These individuals will be advised to watch for respiratory depression and sedation that occur well before fatal apnea, and how to respond.

While there are no prohibitions on concomitant care, any care or medications unrelated to the trial will be noted in the CRFs for each participant.

Participants are sometimes obtaining respite care at facilities with nursing and physician care. Medical reconciliation is done at each admission. Parents will be provided with a letter to share with these programs outlining the study, the drug being tested, and a 24-hour pager to contact for further information or concerns

Active Participants < 15kg in mg per kg

Day	Morning mg/kg	Noon mg/kg	Evening mg/kg	Total mg/kg per day	% Change
1*	0	0	5	5	0
2	0	5	5	10	100%
3	5	5	5	15	50%
4	5	5	5	15	0%
5	5	5	10	20	33%
6	5	5	10	20	0%
7	5	5	10	20	0%
8	10	10	10	30	50%
9	10	10	10	30	0%
10	10	10	10	30	0%
11	13.3	13.3	13.3	40	33%
12	13.3	13.3	13.3	40	0%
13	13.3	13.3	13.3	40	0%
14	17	17	17	50	25%
15	17	17	17	50	0%
16	17	17	17	50	0%
17	20	20	20	60	20%
18	20	20	20	60	0%
19	20	20	20	60	0%
20	13.3	13.3	13.3	40	-33%
21	6.7	6.7	6.7	20	-50%
22	0	5	5	10	-50%
23	0	0	5	5	-50%
24	0	0	0	0	-100%
25	0	0	0	0	0%
Switch over*	-	-	-	-	-

^{*}Day one or 26 if switching over, not both.

Active Participants > = 15kg in mg per day

Day	Morning mg	Noon mg	Evening mg	Total mg/kg per day	Total mg/day	% Change
1*	0	0	75	5	75	0
2	0	75	75	10	150	100%
3	75	75	75	15	225	50%
4	75	75	75	15	225	0%
5	100	100	100	20	300	33%

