Randomization will be undertaken by the study pharmacist, using a computer-generated randomization. Before the 2 periods (pair of active drug (G) or placebo (P)) the pharmacist will generate a random code indicating whether G or P is to be given first. The randomization table will be kept in the Research Pharmacy office, which has restricted access. In case of a serious adverse event and when necessary, the randomization of any one participant can be unmasked to the Principal Investigator. This will be done through direct contact between the pharmacist and the Principal Investigator.

Study Contacts

Contact with study participants during the trial will consist of online surveys and telephone check ins. Contacts will be scheduled to overlap with changes in dose. Each contact will last approximately 10 minutes. The following study tools will be used at study contacts (see table 4 for a schedule of assessments at the time of study contacts):

- Health Update (Appendix 6) (midway through each sequence and at study end)
- Pain Survey (Appendix) (only on the first or last day of each block, not both)
- NCCPC-R (Appendix 7)
- PROMIS-57 (Appendix 8)
- Adverse Events Log (Appendix 10)
- Concomitant Medications (Appendix 11)

When the participant begins Sequence 2, the drug will be dispensed again in person.

Follow up

Two weeks past Study End the randomization sequence for individual participants will be unblinded and shared with the participants along with their individual results. The results will be presented numerically and graphically. Graphs showing the outcomes over time on the medication and placebo arms, summarizing the dosage used at individual outcome points will be provided. This will allow participants to make decisions regarding continuing gabapentin (in consultation with their primary caregiver) and is in keeping the Strategies for Patient Oriented Research (SPOR) principles that this clinical care trial is based on. At this time, the participant's caregiver will also be given the opportunity to provide feedback to the research team via the Participation Questionnaire (Appendix 9).

For any participant that experiences a SAE, there will be an initial contact at the time of the event and appropriate evaluation undertaken by the physician investigator. Another safety follow-up visit will be scheduled within 7 days following the final study visit to review the event. Additional follow-up may be done based on the investigator's medical judgment.

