6.2. Schedule of Enrolment, Interventions, and Assessments

Gabapentin Trial Diagrams and Summaries

Table 3 shows which assessments happen during specific phases of the trial. Table 4 shows the exact timepoint assessments are administer

Trial Design Summary

- Repeated Measures Single Cross-Over Trial (Treatment and Placebo)
- We will recruit 10 study participants. These participants will have completed the PIUO Pathway without resolution of pain. They will have severe neurological impairment and unexplained, untreated pain.
- The study participants will be randomized to treatment or placebo arms. This first session will take 25 days. During this time the treatment arm gabapentin dose will be slowly increased until an effective dose or maximum dose (60mg/kg/day) is reached, whichever comes first.
- The participants will then undergo a three-day long washout period, where neither drug nor placebo will be administered.
- Following this, the participants that were on placebo previously will switch to gabapentin treatment and those who were on gabapentin treatment will switch to placebo. This will again go on for 25 days, with the gabapentin dose increasing throughout.
- NCCPC-R, PROMIS-57 and Pain Surveys will be administered throughout the trial to obtain data
- The total participant time will be around 55 days.
- The diagram below depicts the Gabapentin trial design.

N-of-1 Design

The Gabapentin Trial will use an N-of-1 design. This means that each participant will be his or her own experiment, acting as both treatment and placebo participants. In an N-of-1 trial, each participant's treatment data is compared to his or her own placebo data, and the results are specific to

the individual participant. A small "N" such as 10 (as we are going to recruit for the Gabapentin Trial) can provide an adequate amount of data when using an N-of-1 design because 10 separate data sets and results will be produced. Multiple N-of-1 trials that are conducted on similar patients taking similar drugs can be amalgamated to give broader results.

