^{*}If the child participated in the PIUO Study within the last 6 months these items will already be completed and only a Health Update is necessary to complete prior to drug dispensing. If the child did not participate in the PIUO Study all items will be completed and the PIUO Pathway will be implemented prior to drug dispensing. If a treatable cause for the child's PIUO is uncovered, the child will be withdrawn from the gabapentin trial.

Version 3.0 October 4, 2020 Page 39 of 45

 Table 4: Medication and Placebo Assessment Schedule for all subjects

Day	Health Update	Concomitant Medications	NCCPC-R	Pain Survey	PROMIS-57
1	X	X	X	X	X
2					
3					
4					
5			X	X	
6					
7					
8			X		
9					
10					
11	X		X		
12			X	X	X
13			X		
14			X		
15			X		
16			X	X	X
17			X		
18			X		

Version 3.0 October 4, 2020 Page 40 of 45

19			X	X	X
20					
21					
22			X		
23					
24					
25					
Switch Over*	X	X	X	X	X

^{*}Day 1 or 26 if switching over, not both

Version 3.0 October 4, 2020 Page 41 of 45

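### Table 4 schedules the Concomitant Medications form at none of the dose increases, although the opioid and CNS-depressant dose rule works only if a newly started drug is known before the next increase

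*Protocol*

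**What the plan says.** Section 3.3 (Concomitant Care) of the Protocol places no restriction on other medicines. It acknowledges respiratory depression with opioids as a serious risk, expects a minority of children to be on opioids, and sets a rule: "Dose adjustments will be added when gabapentin is used with a concomitant opioid or other CNS depressant medication". Under that rule the family goes back one dose step and stays there for the rest of the arm. The same schedule is copied to the other arm to protect the blind.

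Section 3.8 (Study Contacts) describes how staff and families communicate: "Contact with study participants during the trial will consist of online surveys and telephone check ins". It adds: "Contacts will be scheduled to overlap with changes in dose". It then lists the tools used at contacts, with the pointer "see table 4 for a schedule of assessments at the time of study contacts". One entry is "Concomitant Medications (Appendix 11", with no days attached. Another entry does carry a limit: "Health Update (Appendix 6) (midway through each sequence and at study end".

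Section 6.2 gives Table 4 a definite status: "Table 4 shows the exact timepoint assessments are administer". Its columns are "Day Health Update Concomitant Medications NCCPC-R Pain Survey PROMIS-57". The Concomitant Medications column is marked in two rows only, day 1 and switch-over. The footnote reads the switch-over row as day 1 or day 26, not both.

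**The concern.** The rule in section 3.3 is preventive. It tells the family to step back and stop escalating, which can happen only if the new drug is recognised while the dose is still rising. Parents give the doses at home from a daily tracker (sections 3.1 and 3.3), so each planned increase goes ahead unless someone stops it.

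The form that would show a newly started opioid or sedative is not scheduled at any of those increases. If staff work from Table 4, its next use after day 1 comes when dosing in that period is over and the rule can no longer be applied. The protocol itself calls the risk serious.

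**Working it through.** No power or error-rate calculation is involved. The check lists the days on which the total daily dose rises (dosing tables, section 3.3) and compares them with the days marked in Table 4 (section 6.2). Day 1 is the starting dose and is not counted as an increase.

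Table 4 marks:
- Concomitant Medications: day 1 and switch-over (day 26).
- Health Update: days 1 and 11, and switch-over.
- NCCPC-R: days 1, 5, 8, 11 to 19 and 22, and switch-over.

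| | < 15 kg | ≥ 15 kg |
|---|---|---|
| Days on which the dose rises | 2, 3, 5, 8, 11, 14, 17 | 2, 3, 5, 8, 11, 14 |
| Number of increases | 7 | 6 |
| Size of the steps | 5, 5, 5, 10, 10, 10, 10 mg/kg/day | 75, 75, 75, 150, 150, 75 mg/day |
| Total rise | 55 mg/kg/day (5 to 60) | 600 mg/day (75 to 675) |
| Increases with Concomitant Medications | 0 of 7 | 0 of 6 |
| Increases with Health Update | 1 (day 11) | 1 (day 11) |
| Increases with neither form | 7 − 1 = 6 | 6 − 1 = 5 |
| Increases with NCCPC-R | 5 (days 5, 8, 11, 14, 17) | 4 (days 5, 8, 11, 14) |

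Both dosing tables show zero dose on days 24 and 25, so the day 26 mark follows the end of dosing. The scheduled gap between the two uses of the form is 26 − 1 = 25 days.

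**Does the section 3.8 list override Table 4?** The absence of a day limit does not settle it. PROMIS-57 also has none in that list, yet Table 4 confines it to days 1, 12, 16, 19 and switch-over. The Pain Survey is limited in the list to the first or last day of each block, but Table 4 marks it on days 1, 5, 12, 16, 19 and switch-over. The Adverse Events Log is in the list and has no Table 4 column at all. List and table are not reconciled, and neither can be taken as the sole authority.

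**Effect of marking days 5, 8, 11, 14 and 17.** The form would coincide with 5 of 7 and 4 of 6 increases. The intervals between scheduled medication questions from day 1 would be 4, 3, 3, 3 and 3 days. The steps covered are 5 + 10 + 10 + 10 + 10 = 45 of 55 mg/kg/day, and 75 + 150 + 150 + 75 = 450 of 600 mg/day. These are parts of the maximum dose rise, not of the risk. The increases on days 2 and 3 follow the day 1 form by one and two days.

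**The case against.** The strongest reply is that Table 4 is not the protocol's whole provision for learning about medicines.
- Section 3.9 requires source records to hold the start and stop dates and dosing of concomitant therapy, so drugs begun mid-period must be recorded.
- Table 3, allowing for a column apparently lost at the page break, places the form in both sequences and at study end. That fits a running log.
- Adverse events have no Table 4 column either, yet section 3.12 has staff ask about them at each contact. Concomitant Medications may work the same way. PROMIS-57 is a scored questionnaire and so an imperfect comparison.
- Section 3.3 adds medication reconciliation at respite admissions, a letter to those programs, a 24-hour pager, and advice to caregivers on watching for sedation and respiratory depression.
- The Health Update on day 11 falls on an increase and might ask about medicines. Neither that form nor the Concomitant Medications form is shown.

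Much of this stands. A reader might infer that a new opioid would go unnoticed until day 26, or that nobody asks about medicines during titration. The documents do not support that.

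What the reply does not supply is timing. The recording duty in section 3.9 is met by retrospective entry, and the Table 3 row names no days. Section 3.3 gives adverse events as the purpose of the twice-weekly contacts at dose increases, and starting a drug is not an adverse event. Section 2.3 describes the Health Update as a check of known side effects. The respite measures cover respite stays, and watching for sedation detects harm after it has begun.

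A reader might also add that a child already on an opioid at day 1 has no earlier step to return to. That concerns the wording of the rule, not the schedule. Such drugs are listed at baseline, and the matter adds no weight here.

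**Conclusion.** The point holds as a conflict between text and schedule with a safety consequence. A dose rule that depends on prompt knowledge of a new drug has no scheduled medication question at any of the 7 (< 15 kg) or 6 (≥ 15 kg) increases. The next scheduled use of the form comes after dosing has ended. The change should be made, because the risk is one the protocol names and the repair is small. The rule itself is sound, and the gap is only in when the information is collected.

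The counts assume the full schedule. A child held at a lower dose because of clinical effect has fewer increases. The point concerns drugs newly started within a period. The number of children affected cannot be estimated from the protocol, and no rate of harm follows from these counts. Confidence is medium, because the two forms are not shown and staff may ask at contacts without the schedule saying so.

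**What to change.** 1. In Table 4, mark Concomitant Medications (any new, stopped or changed drug) in both periods on days 5, 8, 11, 14 and 17. Day 17 is an increase only for children under 15 kg, but marking it for all keeps one schedule. The answer must come before the first raised dose of that day. From day 8 onward, and on day 5 for children of 15 kg or more, the morning dose already rises.
2. At each dispensing, tell families to call before starting an opioid or other CNS depressant, and to hold the next increase until the investigator has applied the section 3.3 rule. This also covers days 2 and 3 and the days after 17. It matters as well because an online answer may not be read before the dose is given.

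Cost: no new contact day, since each of these days already has an NCCPC-R. With day 17 marked for all, the added load is 5 questions × 2 periods × 10 children = 100 in the whole trial. When a drug is reported, titration may be briefly delayed, possibly within the day 11 to 19 outcome window. The delay must be mirrored in the other period, as section 3.3 already requires for dose changes under this rule.

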3.4. Outcomes

1. Primary Outcome: The mean pain and irritability score on the NCCPC-R through days 11-19 on active drug compared to placebo.

[figure not shown]
An 11-point decrement in the NCCPC-R score with no rebound x 3 days is considered clinically meaningful minimum change (improvement).

Secondary Outcomes:

- 2. For patients who benefited from gabapentin, identification of the lowest dose that was effective in reducing pain scores, as shown by a improvement the NCCPC-R score compared to baseline during day 11-19 on active drug.
- 3. For patients who benefited from gabapentin, identification of the maximal effect dosage as measured by the largest improvement in the NCPCC-R score compared to baseline during days 11-19 on active drug.
- 4. Identification of the latency time in days to the onset of maximum relief of pain and irritability as measured by the NCCPC-R score over days 0-19.
- 5. Adverse Events Collection demonstrates the AE on treatment arm do not exceed the frequency found in the Product Monograph for children receiving gabapentin.
- 6. Exploratory Outcome: PROMIS-57 scores reported by parent/caregiver are improved on the treatment arm compared to the placebo arm.

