Summary: This study uses a rapid and safe dose escalation to the widely accepted therapeutic range where evaluation of response will be undertaken with frequent scoring. Different maximal doses are used for children < or ≥ 15 kg, based on pharmacokinetic data. Doses are titrated to clinical effect or maximum target dose, whichever is lower. Once in the therapeutic range, doses change after 3 days if there is not an adequate reduction in symptoms. For any subject that obtains clinical benefit below maximal dose, then they will be held at that dose for the remainder of that period until such time as the scheduled wean begins. At the end of each treatment period there is a wash-out.

Starting Dose: The starting dose of gabapentin will be 5 mg/kg administered as oral liquid or via gastric or jejunal routes. On Day 1 of the study, the gabapentin will be administered once at bed-time and then increased according to the schedule shown in Table 1.

Dose Escalation: The dose will be increased every 3^{rd} - 4^{th} day in a step wise fashion of 13% - 50%, starting with the evening dose in order to accommodate sedation. The maximum dose for subjects will be as follows: < 15 kg to 60 mg/kg day and \geq 15 kg to 45 mg/kg/day. Dose titration will be to a maximum target dose (based on weight as described, < 15 kg, > 15kg) or to clinical effect, whichever is lower. The dose escalation scheme is based upon expert consensus and personal communication with [name], [name], and upon review with the BC Children's Hospital research pharmacist. \cdot , 56.

Some children with PIUO and SNI have been given gabapentin empirically by their health care provider, often without any subsequent, detailed assessment of benefit. Many times, the medication is continued because of its low side-effect profile and overall safety compared with other analgesics. If a subject is currently on gabapentin at the time of enrolment, and the parent/caregiver wants an evaluation of its effectiveness, then the subject can be enrolled in this study with the following approach:

After appropriate enrolment and consent, the subject will be weaned off of gabapentin, in a stepwise manner with 25% reductions in dose every 3rd day. Once they are no longer on the active drug, they will be randomized to active drug or placebo like all other study participants.

Gabapentin Risks and Precautions

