6	100	100	100	20	300	0%
7	100	100	100	20	300	0%
8	150	150	150	30	450	50%
9	150	150	150	30	450	0%
10	150	150	150	30	450	0%
11	200	200	200	40	600	33%
12	200	200	200	40	600	0%
13	200	200	200	40	600	0%
14	225	225	225	45	675	13%
15	225	225	225	45	675	0%
16	225	225	225	45	675	0%
17	225	225	225	45	675	0%
18	150	150	150	30	450	-33%
19	150	150	150	30	450	0%
20	100	100	100	20	300	-33%
21	100	100	100	20	300	0%
22	50	50	50	10	150	-50%
23	25	25	25	5	75	-50%
24	0	0	0	0	0	-100%
25	0	0	0	0	0	0%
Switch over*	_	-	-	-	_	-

^{*}Day one or 26 if switching over, not both.

Inactive

Day	Morning mg/kg	Noon mg/kg	Evening mg/kg	Total mg/kg per day	% Change
1*	0	0	0	0	0%
2	0	0	0	0	0%
3	0	0	0	0	0%
4	0	0	0	0	0%
5	0	0	0	0	0%
6	0	0	0	0	0%
7	0	0	0	0	0%
8	0	0	0	0	0%
9	0	0	0	0	0%
10	0	0	0	0	0%
11	0	0	0	0	0%
12	0	0	0	0	0%
13	0	0	0	0	0%
14	0	0	0	0	0%
15	0	0	0	0	0%
16	0	0	0	0	0%
17	0	0	0	0	0%
18	0	0	0	0	0%
19	0	0	0	0	0%
20	0	0	0	0	0%
21	0	0	0	0	0%
22	0	0	0	0	0%
23	0	0	0	0	0%
24	0	0	0	0	0%
25	0	0	0	0	0%
Switch over*	0	0	0	0	0%

^{*}Day one or 26 if switching over, not both.

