3.10. Statistical Methods

All data will be entered into a REDCap database, either directly from participants using a web-based entry system, or for those using paper, transferred from data collection sheets by a research assistant. The study cohort will be described in tables with descriptive statistics (mean, median and standard deviation) where appropriate. The primary method of analyzing the data was by systematic visual graphing of the pain scale over the exposure/placebo conditions. This is the method recommended by the CONSORT collaboration, extension for N-of-1 studies (CENT).⁵⁸

Data analysis for the primary outcome will be conducted within each N-of-1 trial and will also be aggregated across trials using measurements taken on days 11-19.

For each individual, the pain and irritability score on the NCCPC-R will be calculated over days 11-19 for both the treatment and control periods. These means will then be compared statistically using a Bayesian model, reporting the posterior mean difference using a non-informative prior for the means and variance. The posterior probability that the mean of the treatment is greater than the mean of the control will also be reported. Because of the use of non-informative priors, this analysis is very similar to a t-test.

We will also aggregate the means across participants using Bayesian linear mixed models in order to compare the average effect of the treatment as well as obtain better estimates of each individual's effect through borrowing of strength from others' data.

Additional analyses

Secondary outcomes will be assessed as follows:

- For each patient who benefits from gabapentin, the lowest dose that was effective in reducing pain scores will be calculated as the lowest dose that gives at least an 11 point reduction with no rebound over 3 days in the NCCPC-R score compared to baseline during day 11-19 on active drug. The set of lowest doses will be summarized descriptively.
- For each patient who benefits from gabapentin, the maximal effect dose will be calculated as the dose that gives the largest improvement in the NCPCC-R score compared to baseline during days 11-19 on active drug. The set of lowest doses will be summarized descriptively.

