- The latency time in days to the onset of maximum relief of pain and irritability as measured by the NCCPC-R score will be the day that gives the largest improvement in the NCPCC-R score compared to baseline during days 0-19 on active drug. The set of latency times will be summarized descriptively.
- Adverse Events will be compared between treatment arms descriptively.
- PROMIS-57 scores reported by parent/caregiver will be computed for each patient on each arm by averaging the scores taken on days 12, 16 and 19 and comparing these mean scores. The differences in mean scores between the treatment and placebo arms will be summarized descriptively.

Analysis population and missing data

For the primary outcome, any missing days will be excluded from calculation of the mean.

For secondary outcomes, missing values will be disregarded in the sense that only observed values will be used to compute the lowest dose, maximal effect dose, latency time and PROMIS-57 mean scores.

Analyses will use the intent-to-treat principle meaning that observations in a period will be ascribed to the treatment to which that period was randomized.

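### The fixed primary window of days 11-19 runs two days into the scheduled wean in the ≥15 kg dosing table, but not in the <15 kg table

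*Protocol*

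**What the plan says.** Section 3.4 sets one primary window for all children: "The mean pain and irritability score on the NCCPC-R through days 11-19 on active drug compared to placebo". Section 3.10 repeats it for the individual analyses and for the pooled one, which is "aggregated across trials using measurements taken on days 11-19". Table 4 in section 6.2, a single schedule for all subjects, has the NCCPC-R on each of those nine days.

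The dosing tables in section 3.3 differ by weight:

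- **<15 kg:** days 17-19 are at the table maximum of 60 mg/kg/day. The first reduction is the day 20 row, "20 13.3 13.3 13.3 40 -33" (percent), that is 40 mg/kg/day.
- **≥15 kg:** days 14-17 are at 675 mg/day. The first reduction is the day 18 row, "18 150 150 150 30 450 -33" (percent), that is 450 mg/day. Day 19 is also at 450.

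Two rules keep some children at a lower dose. A child who benefits below the maximum follows this rule: "they will be held at that dose for the remainder of that period until such time as the scheduled wean begins". For a child who also takes an opioid or another CNS depressant and goes back to the previous dose, "the subject will remain at that dose with no further escalation for the duration of the trial arm".

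Other outcomes use the same days. The lowest effective dose is the "lowest dose that gives at least an 11 point reduction with no rebound over 3 days" within days 11-19, the maximal-effect dose uses days 11-19, and latency uses days 0-19. PROMIS-57 is summarised by "averaging the scores taken on days 12, 16 and 19". The missing-data rule in section 3.10 drops missing days only. Nothing in the protocol shifts the window by weight group or removes wean days.

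**The concern.** Section 3.3 says response is to be evaluated once the child is in the therapeutic range, and it treats the scheduled wean as a separate phase. One fixed window cannot respect both tables when their weans start two days apart. In the ≥15 kg table the window opens on day 11 at 600 mg/day and leaves out days 8-10 at 450 mg/day, yet it takes in days 18-19 at that same 450 mg/day.

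The placebo period has no matching change in active dose. If benefit declines with dose, the contrast is attenuated in one weight group, which is then pooled with a group that is not affected. For the secondary outcomes the problem is misattribution. If benefit instead carries over into days 18-19, the maximal-effect dose or the latency day may be credited to a wean day. A rebound caused by the wean could make a true top-dose response fail the 3-day rule. One of the three PROMIS-57 days (day 19) is also a wean day for these children.

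**Working it through.** The plan states no figure of its own here; section 3.6 says no power calculation was made. The check is a count from the tables, followed by a range for the effect on the mean.

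**1. Count of wean-day scores.** Inputs: the section 3.3 dosing tables and the Table 4 NCCPC-R days. For a child held at dose h, daily dose = min(h, table dose). A day counts as reduced if it is on or after the first wean day and the dose is below h.

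| Group | First wean day | Reduced days in 11-19 |
|---|---|---|
| <15 kg, any dose level | 20 | 0 of 9 |
| ≥15 kg, at 450 mg/day or less | 18 | 0 of 9 |
| ≥15 kg, at 600 or 675 mg/day | 18 | 2 of 9 (22%) |

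**2. Mean dose, ≥15 kg.**

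- Child reaching 675: (3×600 + 4×675 + 2×450)/9 = 5400/9 = 600 mg/day over days 11-19. Over days 11-17 it is 4500/7 = 642.9. Ratio 0.933.
- Child held at 600: (7×600 + 2×450)/9 = 566.7 against 600. Ratio 0.944.

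**3. Attenuation.** Let f be the mean effect on days 18-19 as a share of the mean effect on days 11-17. The 9-day mean keeps (7 + 2f)/9 of the days 11-17 effect, so the loss is 2(1 − f)/9. The documents give no value for f, so a range is shown:

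| Assumption | f | Loss |
|---|---|---|
| Benefit fully persists | 1 | 0% |
| Effect tracks dose, child held at 600 | 450/600 = 0.75 | 5.6% |
| Effect tracks dose, child at 675 | 450/642.9 = 0.70 | 6.7% |
| Half of benefit left | 0.5 | 11% |
| None left | 0 | 22% |
| Response still building | 1.1 | gain of 2.2% |

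A rebound (f below 0) would exceed 22%. For a true 11-point effect on days 11-17, the 9-day mean shows 9.8 points at f = 0.5 and 8.6 at f = 0. The pooled loss scales with the share of affected children, which is not given: at 6.7% per affected child it is 3.3% if half are affected and 6.7% if all are.

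**4. Three-day rule at 675 mg/day.** Counting forward from the first response day (section 3.10 does not define the start), runs beginning on days 14, 15, 16 and 17 contain 0, 0, 1 and 2 wean days.

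**5. Precision cost of using 7 days instead of 9.** Within-child standard error ratio:

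- Independent days: √(9/7) = 1.134.
- AR(1) with correlation 0.5: the variance of the period mean is 0.3476 (7 days) and 0.2840 (9 days), in units of the day-to-day variance, so √(0.3476/0.2840) = 1.106.

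Signal-to-noise improves only if f is below (9/ratio − 7)/2, which is 0.469 and 0.568.

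At group level, with all children affected and t = between-child SD of the effect divided by day-to-day SD (an assumption), the ratio is √[(t² + 2v₇)/(t² + 2v₉)], where v₇ and v₉ are the variances of the 7-day and 9-day means in the same units:

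| Correlation | t | SE ratio | Break-even f |
|---|---|---|---|
| 0 | 0.5 | 1.065 | 0.725 |
| 0 | 1 | 1.026 | 0.887 |
| 0.5 | 0.5 | 1.075 | 0.687 |
| 0.5 | 1 | 1.040 | 0.828 |

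**The case against.** The strongest reply is that the window was never restricted to the top dose. It includes titration steps in both tables. For children reaching the maximum, mean dose on days 11-19 is (3×40 + 3×50 + 3×60)/9 = 50 mg/kg/day, or 83% of 60, in the <15 kg table, and 600/675 = 89% in the ≥15 kg table even with days 18-19 included. Cutting to day 17 raises the latter to 95% and widens that gap. This is correct, and it means the lighter group is not better exposed overall. It does not turn wean-day scores into scores at the dose under evaluation.

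Second, if effect tracks dose (f = 0.70), dropping two days worsens within-child signal-to-noise, since break-even is about 0.47 to 0.57. That stands. The case for the change is removing a possible bias, not gaining precision. At group level f = 0.70 gains in three of the four assumed cases.

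Third, children are still on active drug on days 18-19, so the wording of the outcome is not literally broken, and no passage says 450 mg/day is ineffective. True, but one window still meets two different wean days.

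Fourth, the ≥15 kg table gives flat milligrams, and its mg/kg column fits only a 15 kg child, whereas section 3.3 states that group's maximum per kilogram. If dosing is per kilogram, the 33% step on day 18 remains but the 450 mg/day threshold does not describe heavier children. Nor does the protocol say how the wean applies to a child held below the maximum. These limits on who is affected should be noted.

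Finally, attenuation needs a fast offset and carry-over a slow one, so these are alternatives within a child. Section 2.3 has placebo given on the same schedule, so reactions to a visible step-down should occur in both periods. Section 3.10 names visual graphing as the primary method, which might reveal a day 18-19 change, but the stated mean over days 11-19 would still include it.

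**Conclusion.** The mismatch is real and follows from counting: 2 of 9 primary scores fall on reduced-dose days for ≥15 kg children above 450 mg/day, 0 of 9 otherwise. That count is firm, subject to reading the ≥15 kg table in milligrams as printed. The consequence is less certain. Loss of effect in affected children runs from 0% to 22%, with 5.6-6.7% if effect tracks dose, more if symptoms rebound, and a reversed sign if response is still building. All of these depend on f, which the protocol cannot supply. This should be fixed because it is an avoidable distortion of the primary endpoint in one weight group, but it does not by itself invalidate the trial.

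**What to change.** Reconcile the window in sections 3.4 and 3.10 with the ≥15 kg table by a short amendment. Without altering any dosing:

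- End the primary window on the last day before the scheduled wean in the child's own table: day 17 for ≥15 kg, day 19 for <15 kg. Use the same days in that child's placebo period.
- Exclude wean days when assigning the lowest effective dose, the maximal-effect dose and the latency day, and from the PROMIS-57 mean.
- Keep days 11-19 for everyone as a sensitivity analysis.
- Do not cut to days 11-17 for all children: the <15 kg table reaches its maximum only on days 17-19, so two of those three days would be lost.

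Costs, all in the ≥15 kg group unless noted:

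- The within-child standard error rises 11-13%. The group standard error rises about 3-7% under the assumptions above.
- A response first seen on day 16 or 17 no longer has three days inside the window and should be reported as unconfirmed.
- The PROMIS-57 mean rests on two scores instead of three.
- Window length differs between the weight groups, which the report must state.
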